10.2.2 Secondary Analyses

Radiologist Preference

The secondary analysis will be to estimate the receiver operating characteristic (sensitivity and specificity) curve for the acoustic angiography system, with an additional aim of evaluating reader preference for specific breast lesion characteristics. Specifically, to compare the diagnostic performance, we will non-parametrically calculate the area under the ROC curve for each reader and each modality, where the ROC curve is derived using the different cut-off of the probability scores across 60 patients. We then fit a mixed effect model, where the outcomes are the estimated area under the ROC curves and the fixed effect is the dummy variable of the acoustic angiography system vs. conventional b-mode ultrasound. The readers will be treated as random effect. F-test from model fitting will be used to test whether the acoustic angiograph has a significant larger AUC than the conventional b-mode ultrasound (with significance level 0.05).

To assess the reader preference for modality for each characteristic including shape, margins and vascularity, we will fit a random effect model with only intercept and random terms for patients and readers while the outcomes are the confidence scores (-3 to +3) . By testing the intercept significantly larger than zero, we will conclude that the new modality provides more confidence for readers than the conventional one.

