2.2 Secondary Objectives

- 2.2.1 To compare the area under the curve (AUC) of acoustic angiography to the AUC of the b-mode ultrasound
- 2.2.2 To compare radiologist preference of acoustic angiography to conventional b-mode ultrasound for each lesion characteristic (shape, margins, and vascularity)

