4.6 Reader Study

A total of five readers (radiologists trained in breast imaging) will be recruited to participate in evaluation of all imaging performed under LCCC1748.

In the reader preference study, each reader will be asked to compare the acoustic angiography case to the conventional b-mode ultrasound case to evaluate the imaging characteristics based on the BIRADS ultrasound lexicon

(<http://www.acr.org/~media/ACR/Documents/PDF/QualitySafety/Resources/BIRADS/USLexiconClass.pdf>). Specifically the relative ability to evaluate shape, margins and vascularity will be evaluated using a seven-point scale (-3 to +3) for the paired modality comparisons for each of the 60 cases. The order that the modalities will be presented to the radiologists are randomized. The first modality presented for the specimen will be considered the primary and the second modality presented will be considered the secondary for the survey instrument. After a washout period of four weeks, the modalities will be presented in reverse.

The data collection form for the reader study portion is given in Appendix A, section 13.1.

The readers will be asked to assign a subjective malignancy score (-2 (highly not malignant) to +2 (highly malignant)) and their confidence for each lesion for each modality (0 to 100%). These will also be documented on the form in Appendix A. These scores will be used combined for a binary analysis. Malignancy scores of +1 and +2 will be considered malignant. Scores of -2, -1, and 0 will be considered not malignant. The confidence of malignancy will be used independently in the analysis.

5.0 Research Ultrasound Scanner: Verasonics Vantage 256

The device used for this study will be a programmable research ultrasound scanner (Vantage 256, Verasonics, Inc., Kirkland, WA, USA) and a unique probe developed in conjunction with the research lab run by [name] (Sunnybrook Research Institute, Toronto, ON, Canada) and VisualSonics (FUJIFILM VisualSonics, Inc., Toronto, ON, Canada). The ultrasound probe developed is a modification of a preclinical high frequency transducer, modified to house a dual-frequency linear array.

The Vantage 256 is a programmable research ultrasound system. It is marketed commercially by Verasonics, Inc. For this study, two Vantage 256 platforms will be used. Each system will be programmed for

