10.1 Sample Size and Accrual

10.1.1 Primary analysis

For power calculation, the null hypothesis is that the specificity of acoustic angiography system is the same as the standard of care (b-mode ultrasound), which is assumed to be 70%. (We will determine the specificity of b-mode ultrasound during the trial to confirm that the 70%

represents the specificity in the hands of UNC radiologists) Under the alternative, we expect that the specificity of the new device is at least 90%. The specificities are measured relative to pathological diagnosis as the reference standard. With 60 lesions and 5 readers, where we anticipate that roughly half will be malignant, assuming the correlation from the same patient to be 0.5 and the readers to read different patients independently, the power to see specificity at least larger than 90% is 88% (the variance of the estimated specificity is calculated to be less than $0.6^2 \cdot 0.25/30$) at the significance level 0.05 using one-side test. Although we will study both sensitivity and specificity, our power calculation is based on specificity.

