10.1.2 Secondary Analysis

Sixty (60) women scheduled to undergo breast biopsy based on an abnormal ultrasound finding will be enrolled. We assume the AUC for the b-mode ultrasound images is 60% with range 60%~80%, and AUC difference of 10%. Assuming that the prevalence of noncancerous lesions in the sample population will be approximately 50%, the study will be powered at least at 80% with 56 patients and 5 readers.

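### The AUC F-test carries reader variance but not lesion-sampling variance, so its two-sided error exceeds 5% if readers' AUCs covary more within a modality than across modalities

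*Combined protocol and SAP*

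**What the plan says.** Secondary objective 2.2.1 is this comparison: "To compare the area under the curve (AUC) of acoustic angiography to the AUC of the b-mode ultrasound". Under 4.6, five radiologists "will be recruited to participate in evaluation of all imaging performed under LCCC1748", so each of them reads the same lesions. Section 10.2.2 derives a non-parametric AUC for each reader and modality over the 60 patients, then: "We then fit a mixed effect model, where the outcomes are the estimated area under the ROC curves". The fixed effect is modality. On the random side it says only: "The readers will be treated as random effect". The test is stated as: "F-test from model fitting will be used to test whether the acoustic angiograph has a significant larger AUC than the conventional b-mode ultrasound", at level 0.05.

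For power, 10.1.2 assumes a b-mode AUC of 0.60 (range 0.60 to 0.80), a 0.10 difference and about half the lesions benign, and concludes that "the study will be powered at least at 80% with 56 patients and 5 readers". It states no AUC correlation, reader variance or test.

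The other two analyses do bring in patients. The primary analysis in 10.2.1 bootstraps patients for sensitivity and specificity, and the preference model in 10.2.2 has a random patient term. Neither applies to the AUC test.

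**The concern.** Lesions that happen to suit one modality move all five of that modality's AUCs together. The planned model sees five readers agreeing on a modality difference and counts the agreement as evidence, although part of it may come from which 60 lesions were enrolled. The part of the lesion effect common to both modalities cancels in the paired comparison; the part specific to one modality does not. At stake is the only test of objective 2.2.1: a larger AUC could be declared for acoustic angiography more often than the stated level allows.

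**Working it through.** **Inputs from the documents.** 5 readers, 2 modalities and 60 lesions (4.6, 10.2.2); level 0.05 (10.2.2); AUC 0.60 to 0.80, difference 0.10, 56 patients, about half benign (10.1.2). The only correlation in the plan, "assuming the correlation from the same patient to be 0.5", belongs to the specificity calculation in 10.1.1. Using 0.5 as a between-reader correlation for AUC ratings is an assumption made here, as are all the other variance components below.

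**The plan's own figure.** The 80% power cannot be reproduced uniquely. Take Hanley-McNeil variances with 28 malignant and 28 benign lesions (0.00577 at AUC 0.60, 0.00491 at 0.70). Suppose no lesion covariance between readers and no reader-by-modality variance, and let r1 be the same-reader, cross-modality correlation. Then Var(difference) = 0.00577 + 0.00491 - 2 r1 x sqrt(0.00577 x 0.00491), and the F(1,4) test has noncentrality 5 x 0.10² / Var(difference). Power for 0.60 v 0.70 is about 38% at r1 = 0, 50% at 0.3, 63-64% at 0.5 and 83-84% at 0.7. So 80% is reachable under some assumptions and not under others.

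**Expected mean squares with no true difference.** Let Cov1 be the covariance of one reader's AUCs in the two modalities, Cov2 that of two readers in the same modality, and Cov3 that of two readers in different modalities. Let s²TR be the reader-by-modality variance and s²e the AUC error variance.

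- E[MS(modality)] = s²TR + s²e - Cov1 + 4(Cov2 - Cov3)
- E[MS(reader x modality)] = s²TR + s²e - Cov1 - (Cov2 - Cov3)
- Difference = 5(Cov2 - Cov3)

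The planned ratio is therefore distributed as (1 + r) x F(1,4), with r = 5(Cov2 - Cov3) / E[MS(reader x modality)]. The 5% critical value of F(1,4) is 7.709, so the two-sided false-positive rate is P(F(1,4) > 7.709/(1 + r)).

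| r | Two-sided | False claim for acoustic angiography |
|---|---|---|
| 0 | 5.0% | 2.5% |
| 0.25 | 6.8% | 3.4% |
| 0.5 | 8.6% | 4.3% |
| 1 | 12.1% | 6.1% |
| 2 | 18.4% | 9.2% |

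The right-hand column passes 5% when the two-sided rate passes 10%. The 10% critical value is 4.545, so this needs r above 7.709/4.545 - 1 = 0.70.

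**What r might be.** Illustration by simulation: latent-normal ratings, 30 malignant and 30 benign lesions, AUC 0.7, assumed between-reader correlation 0.5. The table gives the simulated r and the closed-form rate.

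| Reader-by-modality SD (latent) | Cross-modality 0.40 | Cross-modality 0.25 |
|---|---|---|
| 0 | r = 1.0, 12.1% | r = 2.5, 21.2% |
| 0.3 | r = 0.27, 6.9% | r = 0.67, 9.8% |
| 0.5 | r = 0.12, 5.9% | r = 0.29, 7.1% |

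The simulated rates agree within about a point: 12-22%, 7-10% and 6-7% by row. With cross-modality correlation also 0.50, so that nothing is specific to a modality, the rate is 5%.

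**Estimation method.** The plan names no denominator df. If a REML fit estimates the reader variance as zero and pools the error on 8 df, the rate rises: simulated 10.3% instead of 8.1%, and 15.7% instead of 12.5%, when the AUC correlations behind Cov2 and Cov3 differ by about 0.05 and 0.10.

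**Corrected test.** Adding 5 x max(Cov2 - Cov3, 0) to the denominator, with covariances estimated from the lesions and adjusted df, held the rate at 4.2-5.7% across 11 null settings in which the planned F(1,4) test gave 4.7-28.3%.

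**The case against.** The strongest reply is that the documents do not establish Cov2 > Cov3. Acoustic angiography is acquired together with b-mode, and readers score both on one form, which could bring Cov3 up towards Cov2. It could also raise the same-reader correlation, which shrinks the denominator and works the other way. This stands: the condition is plausible, because the contrast image is meant to show microvasculature that b-mode does not (1.3.1), but it is not documented.

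Second, the high rates need all five radiologists to gain almost equally from the new modality. This also stands: with latent SD 0.5 the rate is only 6-7%.

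Third, the wording of the claim is directional and the primary power calculation is one-sided at 0.05. Against a 5% limit on false claims for acoustic angiography, the planned test fails only when r exceeds about 0.7. That is correct, but a one-df F-test at 0.05 is two-sided, and a one-sided 5% test would be inflated too whenever r is above zero.

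The repeat reading ("After a washout period of four weeks, the modalities will be presented in reverse") does not help: the lesions are the same, and averaging readings would reduce reader noise and could raise r.

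A reader might infer that the test is valid only for these particular 60 lesions, or that shared lesions alone inflate it. Neither follows. If Cov2 equals Cov3, the balanced test holds 5% for the wider lesion population as well.

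**Conclusion.** The omission is real and its direction is conditional. As written, the balanced F(1,4) test keeps its level beyond these lesions only if Cov2 does not exceed Cov3; if it does, the two-sided rate is above 5% by an amount fixed by r, which the documents do not give. Under the assumed correlations it runs from about 6% to 22%. The algebra is exact; the sizes rest on assumed variance components.

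Two stronger conclusions are tempting. One is that the true error is 12-22%; that needs no reader-by-modality variation, which nothing in the plan supports. The other is that the 80% power is wrong; it is neither confirmed nor refuted, because its inputs are not stated.

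Only secondary objective 2.2.1 is affected. The primary comparison resamples patients and is untouched. The point should be fixed before the reader scores are analysed.

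**What to change.** In 10.2.2, keep the reader AUCs but test them with a multi-reader method that carries both reader and lesion variance. One option is the Obuchowski-Rockette test, F = MS(modality) / [MS(reader x modality) + 5 x max(Cov2 - Cov3, 0)], with covariances estimated from the same lesions and scores as the AUCs (for example by DeLong) and Hillis denominator df. Another is a bootstrap that resamples patients, as 10.2.1 already does, and also accounts for readers. Claim a larger AUC only if p < 0.05 and the difference favours acoustic angiography. Base the power statement in 10.1.2 on the chosen test and write down its assumed correlations and reader variation.

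The cost is SAP wording and standard software, with no new data. The test is stricter. With 28/28 lesions, the same assumed between-reader correlation of 0.5 and no reader-by-modality variation, power for 0.60 v 0.70 falls from 65% to 56% at cross-modality correlation 0.40, and from 62% to 38% at 0.25. For 0.80 v 0.90 it falls from 87% to 83% and from 82% to 66%. These losses are largest where the planned test's error is most inflated; with latent SD 0.5 the two tests differ by about 2 points or less.

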13.0 APPENDICES

13.1 Appendix A: Reader Study Data Collection Form

Specimen: _____

Reader: _____

Date: _____

Overall Assessment:

Primary

Overall specimen malignancy score (-2 to +2): _____

Malignancy confidence (0-100) _____ %

Secondary

Overall specimen malignancy score (-2 to +2): _____

Malignancy confidence (0-100) _____ %

1. Primary versus Secondary Shape/Morphology

+3	I am significantly more confident in the Primary representation of the lesion shape/morphology I described as compared to Secondary representation of the same lesion
+2	I am more confident in the Primary representation of the lesion shape/morphology I described as compared to Secondary representation of the same lesion
+1	I am slightly more confident in the Primary representation of the lesion shape/morphology I described as compared to the Secondary representation of the same lesion.
0	I have the same confidence in the Primary representation of the lesion shape/morphology I described as I do in the Secondary representation of the same lesion
-1	I am slightly less confident in the Primary representation of the lesion shape/morphology I described as compared to the Secondary representation of the same lesion.
-2	I am less confident in the Primary representation of the lesion shape/morphology I described as compared to the Secondary representation of the same lesion.
-3	I am significantly less confident in the Primary representation of the lesion shape/morphology I described as compared to the Secondary representation of the same lesion.

2. Primary versus Secondary: Vascularity

+3	I am significantly more confident in the Primary representation of the lesion vascularity I described as compared to the Secondary representation of the same lesion.
+2	I am more confident in the Primary representation of the lesion vascularity I described as compared to Secondary representation of the same lesion
+1	I am slightly more confident in the Primary representation of the lesion vascularity I described as compared to the Secondary representation of the same lesion.
0	I have the same confidence in the Primary representation of the lesion vascularity I described as I do in the Secondary representation of the same lesion.
-1	I am slightly less confident in the Primary representation of the lesion vascularity I described as compared to the Secondary representation of the same lesion.

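### The preference test in section 10.2.2 reads a positive intercept as favouring acoustic angiography, but the scores are signed by order of presentation and are never re-signed by modality

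*Combined protocol and SAP*

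**What the plan says.** Objective 2.2.2 is "To compare radiologist preference of acoustic angiography to conventional b-mode ultrasound for each lesion characteristic", the characteristics being shape, margins and vascularity.

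Section 4.6 (Reader Study) sets up the comparison. Five readers score 60 cases on a seven-point scale from -3 to +3. On order it says "The order that the modalities will be presented to the radiologists are randomized" and "The first modality presented for the specimen will be considered the primary"; the second modality shown is the secondary. It then says "After a washout period of four weeks, the modalities will be presented in reverse".

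The Appendix A form fixes the sign. For shape, +3 reads "I am significantly more confident in the Primary representation of the lesion shape/morphology" relative to the Secondary, and negative scores mean less confidence in the Primary. Vascularity and margins are scored the same way. The form header has fields for specimen, reader and date only.

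Section 10.2.2 takes the -3 to +3 scores as the outcome of a model with an intercept and random patient and reader terms, and nothing else. Its decision rule is "By testing the intercept significantly larger than zero, we will conclude that the new modality provides more confidence for readers than the conventional one".

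**The concern.** The form score says whether the reader preferred the image shown first. The decision rule treats the same number as saying whether the reader preferred acoustic angiography. The two agree only if acoustic angiography is always shown first, and section 4.6 rules that out by randomising the order and then reversing it. No section multiplies the score by -1 when b-mode was Primary, and the model has no modality or order term.

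If the scores are analysed as defined, a real preference for acoustic angiography gives a null result for objective 2.2.2. A tendency to favour whatever is shown first would be reported as a preference for the new modality, even if readers preferred b-mode.

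**Working it through.** The documents give no power, effect size or variance for this test, so there is no figure to reproduce.

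**Algebra (no assumed values).** Let d be the preference for acoustic angiography in points, o the tendency to favour the image shown first, and s = +1 if acoustic angiography is Primary, -1 if b-mode is. The form score is y = s·d + o + error. The reversal in section 4.6 gives each reader and lesion one session with s = +1 and one with s = -1.

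- As coded, both sessions: [(d + o) + (-d + o)]/2 = o.
- Re-signed (s·y), both sessions: [(d + o) + (d - o)]/2 = d.

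For example, with d = 1 and o = 0 the two session means are +1 and -1, and the pooled intercept is 0. Re-signed, they are +1 and +1, and the intercept is 1.

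**Simulation (for size only).** From the documents: 60 lesions, 5 readers, two reversed sessions, integer scores limited to -3 to +3, random patient and reader terms. Assumed: SDs of 0.5 (patient), 0.3 (reader), 0.5 (reader-by-patient) and 1.0 (residual); order randomised per lesion; one-sided 0.05, since section 10.2.2 gives no level for this test. There were 1,000 trials per setting.

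No first-shown effect:

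| True preference d | As coded: mean | As coded: claims | Re-signed: mean | Re-signed: claims |
|---|---|---|---|---|
| 0.5 | 0.00 | 1.4% | 0.49 | 87% |
| 1 | 0.00 | 0.8% | 0.98 | 99.9% |
| 2 | 0.00 | 0.0% | 1.85 | 100% |

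Claims fall as d grows because the scores at +d and -d cancel in the mean but inflate the residual variance.

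No true preference, over an assumed range of first-shown effects:

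| First-shown effect o | -0.3 | -0.1 | 0 | +0.1 | +0.2 | +0.3 |
|---|---|---|---|---|---|---|
| As coded: claims | 0% | 0% | 2% | 55% | 98% | 100% |
| Re-signed: claims | 5-6% | 5-6% | 5-6% | 5-6% | 5-6% | 5-6% |

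Randomising order per read or per reader gave the same pooled pattern.

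**Second simulation, other assumptions.** Patient SD 0.7, reader 0.3, residual 1.0, order randomised per read, 4,000 runs. With both sessions as coded and o = 0, the mean intercept was 0.00 and claims were 1.0-1.5% for d = +1, 0 and -1. With o = 0.3, the mean was 0.28-0.30 and claims were 100% for all three, including d = -1, where readers prefer b-mode. Re-signed, the means were about 0.97, 0.00 and -0.97 with or without the order effect, and claims were 100%, about 5% and 0%.

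**If only session 1 is analysed.** Section 10.2.2 does not say which sessions enter. In one session the preference cancels only in expectation. If order were randomised per reader, five readers could not split evenly. With d = 1 and o = 0, the 32 possible patterns give an expected mean of ±0.2 (probability 20/32), ±0.6 (10/32) or ±1.0 (2/32).

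**The case against.** The best defence is that re-signing is obviously intended. Section 4.6 describes the scale as a comparison of acoustic angiography with b-mode, and section 10.2.2 speaks of preference for modality and of the new modality. Primary and Secondary may be no more than labels for filling in the form. The malignancy and confidence scores sit on the same form under the same labels, and sensitivity, specificity and AUC cannot be computed per modality without decoding them. A key to the order must therefore exist, and an analyst would have to apply it to half the form and ignore it for the other half. The false-claim rates also rest on a first-shown effect and variances that appear nowhere in the documents.

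Much of this stands. The intention is probably as described, the order is probably recoverable from the randomisation allocation, and the false-claim rates are illustrative. But describing the scale as a paired comparison of modalities does not give it a sign. The only sign in the documents is Primary versus Secondary, and section 10.2.2 names those scores as the outcome of a directional test. The cancellation needs no assumed value.

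The phrase in section 10.2.1 about five ratings per patient might suggest one rating per reader, but it concerns the primary analysis and does not settle which sessions enter the preference model.

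**Conclusion.** The point holds. As written, the intercept in section 10.2.2 estimates the first-shown effect and not the preference named in objective 2.2.2. With both sessions pooled, the preference cancels exactly (apart from rounding and the limits of the scale), whatever the variances. Under the assumed SDs, a true preference of 0.5 to 2 points would be claimed in at most 1.4% of trials, against 87% or more after re-signing. Claims of preference when there is none rise above the nominal 5% with pooled sessions only if readers favour the first image; the size of that effect is unknown.

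The scope is one secondary objective. The sensitivity, specificity and AUC analyses do not use this model, though their scores need the same order key. This should be fixed, preferably before reading starts and in any case before analysis.

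**What to change.** - In section 10.2.2, define the preference outcome as acoustic angiography minus b-mode: the form score, multiplied by -1 when b-mode was Primary. Test the intercept of that score.
- State that both sessions are analysed. With full reversal the order effect then averages out and no order term is needed. If one is added, code it +1/-1 so that the intercept remains the average preference. With d = 1 and o = 0.3, a 0/1 indicator would make the intercept 1 + 0.3 = 1.3 or 1 - 0.3 = 0.7, depending on the reference order.
- A reader-by-patient random term, for the two scores from each reader on each lesion, is optional.
- Add the Primary modality and the session to the Appendix A form, or link the form explicitly to the randomisation list. Use the same key for the malignancy and confidence scores.

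The cost is a few sentences and two form fields (or one stated link), with no extra reads or patients.
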